4.2. Exclusion Criteria

Subjects meeting any of the following criteria will not be included in the study:

1. The subject is morbidly obese, defined as Body Mass Index (BMI) of > 40.
2. The subject has a history of total or unicompartamental reconstruction of the affected joint.
3. The subject will be operated bilaterally.
4. Patients who had a Total Hip Arthroplasty (THA) on contralateral and/or ipsilateral side within the last year that is considered to have an unsatisfactory outcome (Patients with

contralateral and/or ipsilateral THA > 1 year ago with good outcome can be included in the study).

5. Patients who had a Total Knee Arthroplasty (TKA) on contralateral side within the last year that is considered to have an unsatisfactory outcome. (Patients with contralateral TKA > 1 year ago with good outcome can be included in the study).
6. Patients who will need lower limb joint replacement for another joint within one year.
7. The subject has had a high tibial osteotomy or femoral osteotomy.
8. The subject has a neuromuscular or neurosensory deficiency, which would limit the ability to assess the performance of the device.
9. The subject has a systemic or metabolic disorder leading to progressive bone deterioration.
10. The subject is immunologically suppressed or receiving steroids in excess of normal physiological requirements.
11. The subject's bone stock is compromised by disease or infection which cannot provide adequate support and/or fixation to the prosthesis.
12. The subject has had a knee fusion to the affected joint.
13. The subject has an active or suspected latent infection in or about the knee joint.
14. Proven or suspected hypersensitivity to one or more than one of the device materials.
15. Female patients planning a pregnancy during the course of the study.
16. The subject is a prisoner.
17. Severe deformities: varus/valgus deformity >10° (mech. axis), bowed femur >20°, flexion contracture >10°

4.3. Discontinuation and Withdrawal of Subjects

The subject's participation in this investigation is voluntary, and the subject has the right to refuse further participation or withdraw from this investigation at any time and without providing a reason.

In the event that a subject is discontinued from the study for any reason, the site will complete a Study Termination form. Subjects may be withdrawn for the following reasons:

- Serious Adverse Event
- Patient Withdrawal
- Revision/Removal of study device
- Lost to Follow-Up
- If, in the Investigator's opinion, continuation in the study would be detrimental to the subject's wellbeing.
- At the specific request of the Sponsor
- Completion of study and final evaluation

If the patient fails to return for their follow-up appointments, every effort should be made to contact the subject to assess their health status. If after attempting to contact the patient

through three documented phone calls. If the patient still does not respond, the patient will be considered as “lost to follow-up”. A Study Termination Form will be completed after notifying Stryker of the patient’s status.

In the event that the subject is discontinued by the investigative site prior to the final study evaluation, the subject is notified that they are no longer in the study and a Study Termination form will be completed.

Following discontinuation, the subject will be seen regularly as considered clinically appropriate. If the discontinuation was caused by an adverse event the subject will be seen regularly until the symptoms have disappeared or are under control, or until feasible treatment has been undertaken. Refusal to participate or early withdrawal from this investigation will not affect the quality or availability of the subject’s medical care.

Subjects withdrawn from the study will keep their subject number. New subjects must always be assigned a new subject number. In the event that the subject withdraws from this investigation, the information that has already been collected will be included in the database and in the final analyses. The subject’s medical records will also be available for monitoring, auditing and inspection purposes.

5. Subject Enrolment

5.1. Subject Recruitment and Screening

Patients will be recruited at the study sites during preoperative visits through normal referral practice. All patients recruited for this study will have the capacity to give their informed consent on the ethics committee approved, study specific Informed Patient Consent Form.

5.2. Patient Informed Consent and Guidelines

The subject will be informed by the Investigator (or his designated representative) of the purpose of the study, study duration, and follow-up schedule. All foreseeable risks and potential benefits, which might occur during and after total knee arthroplasty, will be discussed with the subject.

The subject will be informed that his/her medical records are subject to review by representatives of the sponsor as necessary. The confidentiality of the subject will be maintained at all times. The subject will be told that he/she is free to refuse study participation or to withdraw from the study at any time without compromising future medical care.

All subjects for this study will be provided with a consent form describing this study giving sufficient information for subjects to make an informed decision about their participation in the study.

The informed consent must contain all elements required by local and institutional policies. The document must be translated into the local language(s) applicable in each study site, be understandable to the subject and must specify who informed the subject. When required by local regulations, the person informing the subject must be a physician. This consent form will be submitted with the protocol for review and approval by the IEC/IRB for the study.

All subjects must provide written consent of their willingness to participate in the study after having had adequate time to consider their decision. The formal consent of a subject, using the EC-approved consent form, must be obtained before that subject is submitted to any protocol related procedures that are not part of the subject’s normal care. Written documentation of

consent must be provided on the consent's signature page in addition to a note in the patient medical records indicating the date that consent was obtained. The investigator obtaining the consent must also sign this consent form. The subject or their legal representative should receive a signed copy of the consent.

All patients receive information about the limitation of the study duration to five, optional 7 years.

5.3. Treatment Assignment

All subjects enrolled in this study are assigned to receive the Scorpio NRG Total Knee System.

5.4. Randomization Procedures and Unblinding

This study will enrol under a non-randomized study design.

5.5. Supplies/Device Accountability

The study devices must be stored and handled in accordance with the manufacturer's guidelines. The Investigator will also keep accurate records of the devices assigned to each subject.

The investigator will be asked to attach the labels (with the lot device number), where possible, of the implanted devices to the corresponding patient CRF page in order to keep a tracking of the devices.

6. Evaluations

Subjects will be evaluated preoperatively and at follow-up intervals of three months, one year, three years, five years and an optional seven years (see Tables 1 and 2). Each subject will be followed for a minimum of five years post-implantation. All subject evaluations will be documented by completion of appropriate Case Report Forms.

Table 2 – Evaluation schedule (functional and patient assessment)

Evaluation	Pre-OP	Intra-OP	Prior to discharge	3 months (± 3 weeks)	1 year (± 2 months)	3 years (± 2 months)	5 years (± 3 months)	7 years** (± 3 months)
Demographics	x							
Medical history	x							
Clinical evaluation	x		x	x	x	x	x	x
Surgical details		x						
KSS	x			x	x	x	x	x
Lower Extremity Activity Scale	x			x	x	x	x	x
KOOS	x				x		x	x
SF-36	x			x	x	x	x	x
EQ-5D	x			x	x	x	x	x
*Radiographs: ap, lateral	x		x		x		x**	x
*Radiograph: merchant view	x			x				
*Radiograph: long leg	x			x				

*Radiographs will not go into analysis

**optional

Basic demographic and medical history information are to be collected at the most two months prior to surgery. This information includes age and gender. Height, weight, primary diagnosis, concurrent medical condition and prior treatment to the affected joint are also documented at this time.

6.1. Surgical Procedure

Standard, accepted surgical procedures for total knee arthroplasty will be utilized. The specific surgical procedure performed at each investigative site is to be documented before study start. All study patients are to be operated on according to the relevant site-specific surgical procedure. Any deviations from this site-specific surgical procedure are to be documented.

After surgery, information is to be collected concerning the surgical details and hospital course of the subject. Information such as length of surgery (skin to skin, tourniquet, instrumentation, and anesthetic times); surgical approach; soft tissue released; ASA Classification; range of motion at discharge; intraoperative complications and prosthesis implanted is recorded.

Appropriate postoperative care will be given and is at the discretion of the physician, as is weight bearing schedule.

Rehabilitation time frame and regimen performed at each investigative site is to be documented before study start. All study patients are to be rehabilitated according to the relevant site-specific rehabilitation procedure. Any significant deviations from this site-specific rehabilitation procedure are to be documented.

6.2. Functional Evaluation

All subjects participating in the study are to be evaluated functionally utilizing the KSS, LEAS, KOOS, and EQ-5D preoperatively and at each protocol specified follow-up interval (see Table 2). Clinical assessment is based on an evaluation of pain and function.

Specific parameters include:

- Pain intensity
- Range of motion
- Stability
- Anatomic alignment
- Walking/standing ability
- Stair climbing ability
- Use of walking aids

To allow for accurate measurement of the range of motion a goniometer should be used. It is of particular importance that a sterile goniometer is used during the surgery to measure the intraoperative range of motion.

6.3. Patient Assessment Evaluations

Data will be obtained from the subjects with the use of standard health status questionnaires. The SF-36 is designed to measure overall evaluation of health, functional status and wellbeing from the subject's perspective. The LEAS is designed to measure patient activity. The patient's quality of life will be measured by the KOOS and EQ-5D. Subjects will be asked to complete the questionnaires preoperatively and at each follow-up evaluation interval specified in the protocol (see Table 2).

7. Adverse Events

7.1. Definitions

Adverse Event (AE) – “Any untoward medical occurrence in a subject whether it is considered to be device related or not. An adverse event can therefore be any unfavourable and unintended sign, symptom, or disease developed or worsened during the period of observation in the study, whether or not related to the investigational product”

An Adverse Event could be:

- a new illness
- worsening of an illness
- an effect of the study device including the comparator (if any)
- a combination of two or more of these factors

Surgical procedures themselves are not Adverse Events; they are therapeutic measures for conditions that require surgery. The condition for which the surgery is required is an adverse event if it occurs or is detected during the study period. Planned surgery measures permitted by the study and the condition(s) leading to these measures are not adverse events. If the condition(s) was (were) known before the subject enrolled in the study, this (these) should be recorded in the medical history CRF.

Adverse Device Effect (ADE) – “Any untoward or unintended response to a medical device including any event resulting from insufficiencies or inadequacies in the instructions for use or the deployment of the device and any event that is a result of user error”

Serious Adverse Event (SAE) – An adverse event that:

- Led to a death, or
- Led to serious deterioration in the health of the subject that:
 - resulted in a life-threatening illness or injury.
 - resulted in a permanent impairment of a body structure or a body function.
 - required in-patient hospitalization or prolongation of existing hospitalization.
 - resulted in medical or surgical intervention to prevent permanent impairment to body structure or a body function, or
- Led to foetal distress, foetal death or a congenital abnormality or birth defect.

The term “life threatening” in the definition refers to an event in which the subject was at risk of death at the time of the event. It does not refer to an event that hypothetically might have caused death if it were more severe.

Serious Adverse Device Effect (SADE) – “adverse device effect that has resulted in any of the consequences characteristic of a serious adverse event or that might have led to any of these consequences if suitable action had not been taken or intervention had not been made or if circumstances had been less opportune”

7.2. Recording of Adverse Events

Once the subject has signed the informed consent, information on all adverse events should be recorded immediately in the source document.

Any adverse event which occurs during the reporting period which is related to the device or meets the definition of serious should be documented via a Serious Adverse Event Form. AE's can be documented via an Adverse Event Form. All complications will be treated with appropriate medical care.

Any device-related Adverse Event will be documented in detail as indicated on the CRF. The following information is required:

- Onset date of the AE
- Description of the event (All clearly related signs, symptoms, and abnormal diagnostic procedure results should be recorded in the source document, though they should be grouped under one diagnosis on the CRF)
- Seriousness of the event
- Intensity of the event (mild, moderate or severe; see definitions below)
- Relationship of the AE to the investigational device (see definitions below)
- Any action taken to resolve the AE
- Outcome of the AE (recovered, recovered with sequela, or on going)
- Stop date of the AE if not indicated as on going

7.2.1. Intensity

The investigator is to classify the intensity of an AE according to the following definitions:

Mild: Transient symptoms, no interference with the subject's daily activities.

Moderate: Marked symptoms, moderate interference with the subject's daily activities.

Severe: The subject is unable to perform usual activity.

7.2.2. Relationship

The investigator is to classify the investigational device relationship of an AE according to the following definitions:

Not related: The time between implantation of the investigational device and occurrence or worsening of the AE rules out a causal relationship, and/or another cause is confirmed and no indication of involvement of the investigational device in the occurrence/worsening of the AE exists.

Unlikely: The time between implantation of investigational device and occurrence or worsening of the AE makes a causal relationship unlikely, and/or the known effects of the investigational device provide no indication of involvement in occurrence/worsening of the AE, and another cause adequately explaining the AE is known, and/or regarding the occurrence/worsening of the AE a plausible causal chain may be deduced from the

known effects of the investigational device, but another cause is much more probable, and/or another cause is confirmed and involvement of the investigational device in the occurrence/worsening of the AE is unlikely.

Possibly: An AE that might be due to the use of the device. An alternative explanation (e.g. concomitant drug(s), concomitant disease(s)) is inconclusive. The relationship in time is reasonable; therefore, the casual relationship cannot be excluded.

Probably: An AE that might be due to the use of the device. The relationship in time is suggestive (e.g. confirmed by dechallenge). An alternative explanation is less likely (e.g. concomitant drug(s), concomitant disease(s)).

Definitely: An AE that is listed as a possible adverse reaction and cannot be reasonably explained by an alternative explanation, e.g. concomitant drug(s), concomitant disease(s). The relationship in time is very suggestive (e.g. it is confirmed by dechallenge and rechallenge)

The clinical course of each device-related event should be followed until resolution, stabilisation, or until it has been determined that the study treatment or participation is not the cause.

7.3. Reporting of Serious Adverse Events and Adverse Device Events

7.3.1. Study Sponsor Notification by Investigator

Any serious adverse event or adverse device event must be reported by the Investigator to the Safety Responsible at Stryker by telephone within 24 hours or at the latest on the following working day.

A Serious Adverse Event Form must be completed by the investigator and faxed to Stryker within 3 working days. The reporting language is English. The investigator will keep a copy of this SAE form on file at the study site. Serious Adverse Events should be reported by phone to the Clinical Study Manager and the site specific responsible CRA.

7.3.2. EC Notification by Investigator

Reports of serious adverse events - including follow-up information - must be submitted to the Ethics Committee (EC) as requested by the responsible Ethic Commission. Copies of each report and documentation of EC notification and receipt will be kept in the Investigator Site File and also in the study Master File.

7.4. Period of Observation

For the purpose of the study, the period of observation for collection of adverse events extends from the time the subject gives informed consent until the date of last study visit or last contact with the subject.

7.5. Medical Monitoring

It is the responsibility of the Investigator to oversee the safety of the study at his/her site. This safety monitoring will include careful assessment and appropriate reporting of adverse events as noted above.

8. Risk Assessment

8.1. Risk Category

There is minimal risk associated with participating in this study over and above that of the primary knee arthroplasty procedure.

8.2. Potential Risk

The study involves the routine assessment of a knee arthroplasty procedure. The device under study has been cleared for marketing and has the CE mark. It will be used according to its labelling. Assessment involves questionnaires, patient and physician assessments, and routine x-rays. The information collected will be kept confidential.

Serious complications may be associated with any total joint replacement surgery. These complications include, but are not limited to: infection, genitourinary disorders, gastrointestinal disorders, vascular disorders, including thrombus, bronchopulmonary disorders, including emboli, myocardial infarction and death.

With all implanted devices, asymptomatic, localized progressive bone resorption (osteolysis) may occur around the prosthetic components as a consequence of foreign-body reaction to the particulate matter of metal or ultra-high molecular weight polyethylene (UHMWPE). Particulate is generated by interaction between components as well as adhesion, abrasion, and fatigue. Secondly, particulates can also be generated by third body wear. Osteolysis can lead to future complications, including loosening, necessitating the removal and replacement of prosthetic components.

Early and late loosening of total knee components can occur. Early biomechanical loosening may result from inadequate initial fixation, latent infection, premature loading of the prosthesis or trauma. Late loosening may result from trauma, infection, biological complications including osteolysis or mechanical problems, with the subsequent possibility of bone erosion and/or pain.

Peripheral neuropathies, circulatory compromise and heterotopic bone formation may occur.

Intraoperative fissure, fracture, or perforation of the femur or tibia can occur due to impaction of the component into the prepared femur or tibia. Postoperative femoral or tibial fracture can occur due to trauma, the presence of defects, or poor bone stock.

Metal sensitivity reactions have been reported following joint replacement.

Adverse events may necessitate reoperation, revision and in rare cases arthrodesis of the involved joint, girdle stone or amputation of the limb.

8.3. Protection Against Risks

Patients will be treated in the best medical judgment of the investigator, regardless of the study protocol. If an investigator must deviate from the written protocol to protect the health or wellbeing of the patient, this deviation will be promptly reported to the Ethics Committee and a protocol deviation form shall be completed.

8.4. Potential benefits to the Subject

In addition to the benefits from the primary knee arthroplasty procedure e.g. reduced pain, improved range of motion, there is no guarantee that patients will personally benefit from inclusion in this study. Patients may undergo more thorough screening and follow-up than non-study patients and may benefit from this increased surveillance. This study seeks to provide clinicians information about this system/device by comparing this treatment/device to published results for other treatments/devices. Information gathered in this study may benefit others undergoing this procedure in the future.

9. Statistical Plan

9.1. Statistical Methods

Descriptive statistics will be computed for all baseline conditions and demographic parameters. For parameters represented by continuous variables (e.g., ROM), the summaries will consist of the mean, median, standard deviation, minimum, and maximum values. For categorical variables, the number and percent in each category will be presented. If appropriate, the data will be presented by appropriate subgroups (e.g., centre, gender). Descriptive statistics and statistical comparisons for important demographic, efficacy, and safety variables will be provided in tables.

A survival analysis will be performed to according to the number of revision surgeries.

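### Adverse events other than revision have only a number-and-percent summary, with no fixed time point, although follow-up runs from early withdrawal to an optional seven years (minor)

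*Combined protocol and SAP*

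**What the plan says.** Three parts of the combined protocol and SAP bear on this.

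- **Summary rule (9.1).** After a sentence on baseline and demographic data, and one on continuous variables, the section says: "For categorical variables, the number and percent in each category will be presented". Later in the same paragraph it adds: "Descriptive statistics and statistical comparisons for important demographic, efficacy, and safety variables will be provided in tables". The one time-to-event method follows: "A survival analysis will be performed to according to the number of revision surgeries". It covers revision only, which the Study Summary names as the primary endpoint.
- **Period of observation (7.4).** Adverse events are collected from informed consent "until the date of last study visit or last contact with the subject".
- **Length of follow-up (sections 6 and 4.3).** Visits after surgery are at "three months, one year, three years, five years and an optional seven years". A subject may "withdraw from this investigation at any time and without providing a reason", and in that event "the information that has already been collected will be included in the database and in the final analyses".

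No section states a denominator, a time window, a rate per unit of exposure or a cumulative incidence for adverse events other than revision.

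**The concern.** The end of observation belongs to the individual patient. Someone who withdraws after a few weeks, someone last seen at 5 years and someone who attends at 7 years all stay in the final analysis. A single percentage over all of them counts each as equally observed. Two effects then work against each other: early exits pull the figure below the 5-year risk, and events recorded after year 5, which arise only in patients still followed, push it above. The printed value depends on attendance as well as on the device.

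What is at stake is interpretation. Section 8.4 says the study will inform clinicians by setting this device against published results for others. A published 5-year incidence cannot be compared with a percentage that has no time point. The plan already accepts time-to-event reasoning for revision. Other adverse events are observed over the same unequal follow-up and have no such summary.

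**Working it through.** The plan states no figure for adverse-event incidence, so there is nothing to reproduce. The calculation only illustrates how far a pooled percentage can move.

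**Inputs from the documents:** 250 patients (3.3); minimum follow-up of 5 years and an optional 7-year visit (section 6); 3 patient-decided withdrawals with 220 patients included at the interim analysis (1.3).

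**Assumptions, not in the documents:** a constant first-event hazard h; a share d of patients dropping out evenly over years 0–5, with d from 5% to 25%; a share f of the rest followed to 7 years, with f from 0% to 100%.

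**Formulas**

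- True risk by time t: p(t) = 1 − exp(−ht).
- Average risk observed in dropouts: u = 1 − p(5)/(5h).
- Expected pooled percentage: C = d·u + (1 − d)·[(1 − f)·p(5) + f·p(7)].

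**Worked case, true 5-year risk 10%**

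- 5h = −ln 0.90 = 0.10536.
- u = 1 − 0.10/0.10536 = 0.0509.
- p(7) = 1 − 0.90^1.4 = 0.1371.
- Low extreme (d = 25%, f = 0): 0.25 × 0.0509 + 0.75 × 0.10 = 0.0877, or 8.8%.
- High extreme (d = 5%, f = 100%): 0.05 × 0.0509 + 0.95 × 0.1371 = 0.1328, or 13.3%.
- Middle (d = 15%, f = 25%): 0.15 × 0.0509 + 0.85 × (0.75 × 0.10 + 0.25 × 0.1371) = 0.1005, or 10.1%. With f = 20% it is 9.9%.

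In 250 patients the extremes are about 22 and 33 patients with an event, against 25 at the true 5-year risk.

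**Same formulas for other risks**

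| True 5-year risk | Low extreme | d = 15%, f = 20–25% | High extreme |
|---|---|---|---|
| 5% | 4.4% | 5.0% | 6.7% |
| 10% | 8.8% | 9.9–10.1% | 13.3% |
| 20% | 17.6% | 19.7–20.0% | 26.0% |

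**Using the documented withdrawals.** 3/220 = 1.4%, below the assumed range for d. With d = 1.4% and f = 0, a true 10% prints as 0.0136 × 0.0509 + 0.9864 × 0.10 = 9.9%. With f = 100% it prints as 0.0136 × 0.0509 + 0.9864 × 0.1371 = 13.6%. Low dropout removes the downward error but not the upward one.

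**The case against.** The strongest case against has four parts.

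1. **The rule is implied.** The number-and-percent sentence comes after one on baseline data and does not name adverse events. It reaches them through the later sentence on safety tables. A reader might infer that the plan commits to a percentage of all patients over all follow-up. It does not say so, and tabulating n (%) by visit interval would also comply. This stands: the defect is an unspecified time basis, not a stated wrong one.
2. **The main late device failure is covered.** Section 8.2 warns: "Late loosening may result from trauma, infection, biological complications including osteolysis or mechanical problems". It is tempting to cite this as proof that late safety events in general will be misreported. But the same section links osteolysis and loosening to removal and replacement of components, which is revision, and revision has its survival analysis. No section shows that the remaining events come late. If most of them are perioperative, the effect is smaller than a constant hazard suggests.
3. **The extremes overstate the likely error.** They pair high dropout with no 7-year attendance, or low dropout with full attendance. In the middle the effects nearly cancel. With 250 patients, the exact 95% interval around 10% is 6.6–14.4%, wider than the illustrated range. This stands as to size. It does not remove the problem, because a confidence interval does not supply the missing time point.
4. **No adverse-event comparison is planned.** Section 8.4 is a paragraph on benefit to subjects. It mentions published results without naming adverse events, and adverse-event incidence is not a listed objective. This stands and lowers the priority.

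The interim withdrawals do not settle the matter. Section 1.3 describes early follow-up and says nothing about loss to follow-up or 7-year uptake.

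**Conclusion.** The point holds for adverse events other than revision. Section 9.1 gives them only a number and a percent, on the natural reading of its two sentences together. With observation ending at each patient's last contact, a pooled percentage has no fixed time point and depends on attendance.

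Under the stated assumptions, a true 5-year risk of 10% could print anywhere from 8.8% to 13.3%, and close to 10% when dropout and 7-year attendance offset. The documents give no event rate, dropout rate or 7-year uptake, so neither the size nor the direction of the error in this study can be stated. A reader might infer that the safety results, including revision, will be materially biased. The documents do not support that: revision has its own analysis, and the distortion may be small.

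Priority: minor. It is a reporting gap in a single-arm descriptive study, cheap to close.

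**What to change.** In 9.1, keep n (%) and add the following.

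- For device-related events and, separately, for serious adverse events: cumulative incidence of first event at 1, 3 and 5 years from surgery, with numbers at risk and 95% intervals. Censor at last contact and treat death as a competing event.
- Report events after the 5-year visit separately, with the patients followed beyond that visit as denominator.
- If rates per patient-year are shown, give them by period, for example 0–1, 1–5 and 5–7 years. A single overall rate also shifts with follow-up length when the hazard is not constant.
- State the assumption of non-informative censoring. It needs stating because 4.3 lists serious adverse events and revision among the reasons for withdrawal.

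Section 7.2 expressly requires an onset date for device-related events. The sponsor should confirm that the Serious Adverse Event Form also records it for unrelated serious events.

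Cost: a few sentences in 9.1 and one extra table. No new visits are needed, and no new data if the form already holds the onset date.
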